4.3.3 Safety Variables

1. Adverse events, serious adverse events (SAEs), and discontinuations due to AEs.
2. Risk for bleeding (will be assessed by monitoring hematocrit levels, urine dipstick tests, and any clinical adverse events for bleeding).
3. Physical examination and vital signs.
4. Clinical laboratory parameters: Hematology (RBC count, white blood cell count, hematocrit, Hb, and PLT, etc.) and clinical chemistry (creatinine, total bilirubin, alanine transferase [ALT], and aspartate transaminase [AST], etc.).

5. Viral retention samples:

Blood samples for viral nucleic acid testing (NAT) and viral serology testing will be collected throughout the 30-day follow-up but will be tested only if the subject exhibits clinical signs and symptoms of viral infection during the one-month follow-up period.

5 General Statistical Considerations

All analyses will be conducted using SAS Version 9.4 or higher.

Unless otherwise specified, descriptive statistics will include the number of non-missing observations, mean, standard deviation (SD), median, minimum and maximum values for the continuous/quantitative data, or frequency counts and percentages for categorical/qualitative data.

5.1 Data Handling

Unless otherwise noted, if an observation is missing at a specific scheduled visit/time point, the value at that visit/time point will not be imputed and will be set to missing.

Baseline in general will be defined as the last non-missing measurement taken prior to the start of the study treatment.

For ICU stay duration and length of hospital stay, if the discharge date is beyond the follow-up period and only ‘>1 month’ is recorded then it will be reported as is in data listings; and the date of last follow-up minus the ICU admission date or surgery date, respectively, plus 1 day or 34 days, whichever is longer, will be assigned for the statistical summary and analysis.

If a patient was mis-stratified with regards to myocardial infarction, the patient will be analyzed according to the correct stratum (accurate stratum).

5.1.1 Adverse Events

Treatment emergent adverse events (TEAEs) will be characterized based on AE onset date/time relative to each subject’s study treatment start date/time.

Adverse events with incomplete start dates will be considered TEAEs if:

- Day and month are missing and the year is equal to or after the year of study treatment start date;
- Day is missing, month is present and the year is after the year of study treatment start date;
- Day is missing and the year is equal to the year of study treatment start date and the month is equal to or after the month of study treatment start date;

- Day, month, and year are all missing.

5.1.2 Prior and Concomitant Medications

The following convention will be used for missing or partial end date information in order to determine whether a medication is prior or concomitant:

The unknown portions of a medication end date will be assumed to be as late as possible. If a medication end date is incomplete but the month/year of medication end date is prior to the month/year of the start of study treatment, then the medication will be considered a prior medication. If a medication end date is incomplete but the month/year of medication end date is the same as the month/year of the start of study treatment, then the medication will be considered a concomitant medication. All other incomplete medication end dates and all medications with missing end dates will be assumed to be concomitant medications.

5.1.3 Clinical Laboratory

For the summaries of post-baseline results only measurements from scheduled visits will be considered, although all values will be reported in data listings.

5.1.4 AT Levels

The lower limit of quantification (LLOQ) for AT Level in serum using an antigenic content assay is 20%. All AT Level values obtained in the study are expected to be above LLOQ considering they reflect both endogenous AT and infused AT-III (Human) exogenously.

For summary of AT levels, any missing or not valid concentration values of AT level will be treated as missing without imputation.

5.2 Analysis Populations

Intention-to-treat (ITT) population will include all subjects who are randomized. It will be used for the analyses of inclusion/exclusion criteria and protocol deviation.

Modified intention-to-treat (mITT) population will include all subjects who are randomized, receive any amount of study drug, and are operated on. It will be used for listings and analyses of operative assessment and efficacy data.

Per-protocol (PP) population will include all mITT subjects with no major protocol deviations that might have impact on the primary efficacy assessment (to be defined in a blinded data review meeting prior to database lock), including postoperative AT administration per investigator's discretion. It will be used for the sensitivity analysis of the primary efficacy variable.

Safety population will include all subjects who receive any amount of study drug. It will be used for listings and analyses of demographic and baseline characteristic, serum pregnancy test, medical history, prior and concomitant medication (except heparin use which is considered efficacy data), study drug infusion, treatment compliance, and safety data. Difference between each subject's planned and actual treatments will be summarized in the CSR should there be any.

5.3 Sample Size

Assuming that percentage of subjects with major morbidity composite is 22.0% in Placebo group and 14.3% in AT-III treatment group (i.e., AT-III treatment group has a 35% relative reduction comparing to the Placebo control group), 192 subjects per treatment arm (total 384 subjects) are needed to have 70% power to detect a trend at alpha = 0.15. Considering 5% dropout rate, it is estimated that 404 subjects (202 subjects per treatment arm) need to be randomized.

5.4 Randomization and Blinding

Subjects will be randomized into one of two treatment groups: AT-III (Human) treatment group and Placebo control group. Subjects will be stratified by their previous history of MI. Unblinded pharmacist or designee will obtain the treatment assignment based on a computer-generated randomization schedule.

To minimize the risk of unblinding, all subjects will receive the same total volume for all treatments with no visible differences in the external appearance of treatments, infusion bags will be covered with a non-transparent sleeve, and opaque intravenous (IV) tubing will be utilized. The unblinded study pharmacist, or designee, will prepare investigational product (i.e., AT-III [Human] and placebo) at each site. Monitoring of activated clotting time (ACT) for subject safety can potentially unblind an investigator if performed immediately before AND immediately after investigational product (IP) administration. Thus, to avoid potential unblinding, investigators should restrain from monitoring ACT values immediately before AND immediately after IP administration. Individual ACT determinations before OR after IP administration is not considered as potentially unblinding and is therefore permitted. However, if ACT monitoring is done prior to IP administration care must be taken to ensure blinded study personnel are not unblinded. Grifols Clinical Trial Materials personnel and Grifols Pharmacovigilance personnel will have access or be privy to treatment assignments.

Emergency unblinding instructions will be located in the Pharmacy Manual (to be used only if required).

Investigators must not draw any blood samples for AT levels outside the requirements of the protocol. Results from protocol-specified AT, thrombin-antithrombin complex (TAT), and prothrombin fragment 1+2 (F1+2) measurements will not be provided to the investigator or blinded sponsor personnel in order to ensure maintenance of the treatment blind.

6 Subject Disposition

Subject disposition will include the number and percentage of all subjects screened, in the populations of ITT (randomized), safety, mITT, and PP, and completing the study by treatment group and overall.

The number and percentage of subjects discontinuing from the study will be summarized by reason for discontinuation by treatment group and overall. The number and percentage of screening failures will be summarized for reasons of ineligibility.

Disposition status will be listed for all subjects.

7 Protocol Deviations

Protocol deviations will be identified during the study and evaluated before database lock. The type/category of protocol deviations and severity (i.e., minor or major) will be listed and summarized for ITT population by treatment group and overall.

8 Demographics and Medical History

Demographic (age, age categories [<65 versus ≥ 65 years], gender, race, and ethnicity, previous MI) and baseline characteristics such as weight, height, body mass index (BMI), smoking status, Ejection Fraction, serum pregnancy test, baseline AT activity level (i.e., last available AT activity level before study treatment) (central laboratory) will be listed and summarized using descriptive statistics for safety population by treatment group and overall. AT activity levels (local laboratory) from pre-screening, screening, and pre-randomization for all screened subjects will only be listed.

Medical case and relevant medical history, surgical history, topical hemostats medication history will also be summarized for safety population by treatment group and overall.

9 Treatments and Medications, Operative Assessments

9.1 Prior and Concomitant Medications

Concomitant medications and those taken within the last month (including transfusions of blood or any blood-derived product) prior to the Screening visit must be recorded in the electronic case report form (eCRF). Prior medications are defined as any medication which ended before the start of study treatment. Concomitant medications are defined as any medication which is started on or after the start of study treatment or any medication taken prior to the study treatment and continued after the start of study treatment.

Summaries of all medications taken during the course of the study will be presented in tabular form and coded using Anatomical Therapeutic Chemical (ATC) classification codes via the World Health Organization Drug classification (WHO-Drug) Dictionary. All medications will be summarized for safety population by treatment group and overall and sorted alphabetically by medication class (i.e., ATC Level 2) and medication sub-

class (i.e., ATC level 4). If the ATC Level 4 term is missing, the ATC Level 3 term will be used in the medication summary table and data listing. For the summary tables, if a subject has taken a medication more than once, the subject will be counted only once at the ATC level. All medications will be listed by subject.

Heparin use recorded on the separate Heparin Administration eCRF form will be listed and summarized separately from other medications based on the mITT population, since it is closely associated with efficacy and is not a safety variable in this study.

9.2 Extent of Exposure

For each treatment, total AT-III actual dose (IU), total actual volume infused (mL), study drug infusion duration (min) will be summarized. Actual AT-III Dose (IU) equals to calculated AT-III dose (IU) * total volume infused (mL) / total volume prepared (mL). Duration of infusion (min) is the difference between the infusion end date/time and the start date/time [(infusion end date/time – infusion start date/time)].

9.3 Treatment Compliance

The treatment compliance is calculated as [total volume infused / total volume prepared]*100%. The total volume prepared is calculated based on the subject's weight at screening. Treatment compliance will be listed and summarized by treatment. The numbers of subjects with compliance <80%, >120%, and >=90% will be calculated.

9.4 Operative Assessments

Type of surgical procedure and duration of CPB and aortic clamp will be listed and summarized for mITT population.

10 Efficacy Analysis

10.1 Primary Efficacy Analyses

Number and Percentage of subjects with any component of a major morbidity composite will be summarized by treatment and analyzed using Cochran Mantel Haenszel test adjusting for history of MI based on mITT population. Sensitivity analyses using PP population or mITT population minus subjects with postoperative AT administration per investigator's discretion will also be provided.

Subgroup analyses by age group, gender, and surgery type (isolated CABG vs. all other surgeries per medical review of all surgical procedures) will be performed for both mITT and PP populations, as well as mITT population minus subjects with postoperative AT administration.

10.2 Secondary Efficacy Analyses

All secondary efficacy analyses will be performed by treatment group based on the mITT population. No multiplicity adjustment will be performed.

All AT activity level data will be presented in listings. Postoperative AT levels at the ICU admission will be summarized. The analysis of covariance (ANCOVA) will be used to compare the treatment difference. ANCOVA model will include the AT level as the dependent variable, treatment as the fixed effect and baseline AT level (last available AT level from central laboratory before study drug administration) as the covariate. The same analyses will also be conducted for AT levels at other time points.

The number and percentage of subjects with AT levels of 58% or higher at the ICU admission will be summarized and compared with Chi-square test (or Fisher Exact test as appropriate).

Postoperative chest-drain blood loss in the first 12 and 24 hours after surgery will be listed, and will be summarized and analyzed using group t-test.

All data about transfusion requirements will be listed and summarized for the mITT population. Each blood product (e.g., RBCs, FFP, PLTs, cryoprecipitate, fibrinogen concentrate, PCCs, plasma, and whole blood) will be summarized separately and analyzed using group t-test. Cell saver blood use will also be analyzed. If the assumptions for parametric test are not met, the non-parametric test (Wilcoxon signed rank test) will be used. Shapiro-Wilk test will be used to test the normality.

Duration of ICU stay and the length of hospital stay will be listed and summarized. The non-parametric Wilcoxon rank sum test will be used to compare the treatment difference, and the Hodges-Lehmann estimate and 95% confidence interval (CI) will be provided.

Number and percentage of subjects with each following procedure or morbidity will be separately summarized and analyzed using Chi-square test (or Fisher Exact test as appropriate). Separate listings will be provided, except all-cause postoperative mortality which will be included in the listing of deaths. A separate eCRF page for Stroke was added while the study was underway, including questions of 'Had a stroke?', 'stroke number', 'stroke date/time', and 'stroke type'. For subjects without the Stroke page, all AEs will be evaluated for stroke events by the medical review.

- Need for surgical reexploration
- Low cardiac output syndrome
- Myocardial infarction (MI)
- Stroke
- Acute kidney injury (AKI)
- Arterial or venous thromboembolic events
- Infections
- Prolonged mechanical ventilation (>24 hours)
- All-cause postoperative mortality
- Prolonged ICU stay (>6 days)

11 Safety Analysis

All safety analyses will be performed by treatment, based on the safety population.

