3.1.1 Treatment Administration

Every subject allocated in the AT-III (Human) treatment group will receive, immediately after anesthesia induction, a single dose of AT-III (Human) sufficient to achieve an absolute increase (Δ) of 20% above pretreatment AT levels according to the following formula, where IU means international unit:

$$AT-III \text{ dose (IU) required} = \frac{(20) \times (\text{subject weight in kg})}{1.4}$$

The only variable in the equation is the subject's body weight. For calculating AT-III (Human) dose, subject's weight obtained during the Screening visit will be used. Since the original protocol required that patients have an AT level < 80% for eligibility, the original equation differed (i.e., AT-III dose (IU) required = (100 - actual AT level in subject) x (subject weight in kg) / 1.4), as the aim was to raise AT level to 100%; given the near impossibility to recruit anyone with a subnormal AT level from the general pre-surgical population the above formula was instituted through protocol Amendment 3 (Version 4.0), 2 April 2015.

AT-III (Human) or Placebo (0.9% NaCl) will be prepared according to the volume calculated by unblinded pharmacist or designee.

AT-III (Human) will not be administered postoperatively unless the investigator decides otherwise for clinical reasons (if this is the case, the subject will be excluded from the per-protocol population for efficacy analysis and also from the mITT population as a sensitivity analysis of the primary efficacy variable).

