4.2.2 Secondary Efficacy Variables

1. AT activity (levels) determinations:

To maintain the study blind, No unblinded AT concentration results will be provided to study sites or blinded Grifols personnel until after closure of the study database.

- a. AT activity levels will be measured for both AT-III (Human) treatment and Placebo control groups at the following time points:
 - Prescreening visit (local lab)*
 - Screening visit (local lab)*§
 - Screening visit
 - Preoperatively
 - Immediately before study drug administration
 - Immediately after study drug administration
 - Postoperatively at ICU admission
 - Postoperatively Day 1
 - Postoperatively Day 2
 - Postoperatively Day 3
 - Postoperatively Day 5
 - ICU discharge
 - 1-month follow-up visit

- * Only applicable for subjects undergoing isolated CABG or single valve repair/replacements (will be needed for eligibility only if subject not receiving preoperative heparin [see entry criteria]).
- § This AT (local lab) determination will not be required if the Prescreening visit is conducted.
- b. Percentage of subjects with AT levels of 58% or higher at the ICU admission will be calculated for both treatment groups and compared.

2. **Chest-drain blood loss** (mL) in the first 12 and 24 hours of chest closure is defined as the amount of blood collected in the cardiotomy reservoir from chest closure through the following 12 and 24 hours measured.
3. **Transfusion requirements** will be measured as the number of units of Fresh frozen plasma (FFP), red blood cells (RBCs), platelets (PLTs), cryoprecipitate, fibrinogen concentrate, prothrombin complex concentrates (PCCs), plasma, and whole blood from the day of ICU admission and throughout the follow-up period.

A specific perioperative transfusion algorithm will be applied:

Standardized Transfusion Algorithm

Red blood cells (RBC):

Administration of RBCs should be performed one unit at a time after which the hemoglobin (Hb) levels should be reanalyzed to check the suitability for the next unit.

- Hb <6.0 g/dL (≤ 3.72 mmol/L [millimoles/liter]): Transfusion is mandatory
- Hb = 6.0-8.0 g/dL (3.72-4.96 mmol/L): Transfusion is optional
- Hb = (8.0-10.0 g/dL). Transfusion is acceptable only if clinically justified*
- Hb >10.0 g/dL: Transfusion is not permitted.

* One or more of the following clinical justifications must be provided:

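### The share with AT of 58% or higher at ICU admission is compared without baseline AT and without a stated estimate or interval; the test is valid, but some precision is given up at no saving

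*SAP*

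**What the plan says.** SAP 4.2.2 lists the endpoint under the AT determinations: "Percentage of subjects with AT levels of 58% or higher at the ICU admission will be calculated for both treatment groups and compared". SAP 10.2 assigns the method. The number and share of subjects with "AT levels of 58% or higher at the ICU admission will be summarized and compared with Chi-square test", with Fisher's exact test as the alternative. No covariate, effect measure or confidence interval is named for it.

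In the same section, the continuous AT level at ICU admission is analysed by ANCOVA with "treatment as the fixed effect and baseline AT level (last available AT level from central laboratory before study drug administration) as the covariate". The covariate is therefore already defined and collected; SAP section 8 also summarises it as a baseline characteristic. SAP 10.2 promises a Hodges-Lehmann estimate with a 95% interval for ICU and hospital stay, but nothing comparable for the 58% share.

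On dosing, SAP 3.1.1 states: "The only variable in the equation is the subject's body weight". Secondary analyses use the mITT population, and "No multiplicity adjustment will be performed".

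**The concern.** Protocol 1.2 and SAP section 2 describe the strategy as avoiding postoperative AT that is too low (below 58%) or too high (above 100%). The 58% share is the pre-specified measure of the lower bound. Its useful result is how large the difference is and how well it is known.

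Baseline AT can be expected to be prognostic for this outcome:

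- Inclusion criterion 4 admits some subjects because their AT is below 80%, and others with no AT limit.
- The dose does not depend on baseline AT, so dosing does not even out those differences.
- The rationale for the protocol amendment names intrinsically low baseline AT as one route to very low AT in the ICU.
- The SAP itself chose baseline AT as the covariate for the continuous level.

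Randomization is stratified only by history of MI. Chance imbalance in baseline AT therefore adds random error to the crude difference, which adjustment would partly remove.

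**Working it through.** **Sample size used.** The plan gives no power or precision for this endpoint, so I take the evaluable number from the primary sample size (SAP 5.3: 22.0% vs 14.3%, alpha 0.15, 70% power). With unpooled variance, n = (1.4395 + 0.5244)² × (0.22 × 0.78 + 0.143 × 0.857) / 0.077² = 3.857 × 0.29415 / 0.005929 = 191.4, which rounds up to 192 per arm. This reproduces the plan (pooled variance gives 193), and the stated figure is two-sided. I use 192 per arm below.

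**Inputs from the documents.** In the earlier trial 26% of controls and 0% of treated patients were below 58% at ICU admission (Protocol 1.1; another product, a 120% target and less complex surgery). A 40-60% fall in AT after bypass is called common (Protocol 1.1). The intended rise is 20 points (SAP 3.1.1).

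**Assumptions, not in the documents.** The correlation between baseline and ICU AT; an ICU AT SD of 15 points with normal data; two-sided 0.05 for secondary tests.

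**Check 1: variance.** I simulated 1,500 trials per setting with 26% of placebo below 58%. The crude risk difference was compared with the standardised risk difference from a logistic model on treatment and baseline AT. To convert to interval width, take 26% vs 15% below 58%. The crude half-width is 1.96 × √[(0.26 × 0.74 + 0.15 × 0.85)/192] = 1.96 × 0.0408 = 8.0 points. The adjusted half-width is 8.0 × √(variance ratio).

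| Assumed correlation | Variance ratio | Reduction | Half-width (points) |
|---|---|---|---|
| 0.3 | 0.94-0.96 | 4-6% | 8.0 to 7.8 |
| 0.5 | 0.86-0.89 | 11-14% | 8.0 to 7.4-7.5 |
| 0.7 | 0.69-0.74 | 26-31% | 8.0 to 6.6-6.9 |

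**Check 2: a second model.** Assumed baseline AT mean 80-90 and SD 12-15, fraction retained at ICU 0.50-0.65 (SD 0.08-0.12), and 20 points added in the AT-III arm. These inputs imply correlations of 0.48 to 0.83. The variance reduction was 9% to 39%, and crude and adjusted mean estimates agreed within 0.003. The half-width fell by 0.2 to 2.0 points (for example 7.5 to 7.0; at best 9.1 to 7.1). These inputs put only about 3-50% of placebo subjects at or above 58%. A further run included settings with 62-68% there, nearer the earlier trial's 74% (100% − 26%). At correlations of 0.52-0.80 it gave reductions of 11-34%.

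**Check 3: does significance change?** Power at 192 per arm, from the model in Check 1:

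| Shift at ICU (points) | Chi-square | Adjusted, correlation 0.3 / 0.5 / 0.7 |
|---|---|---|
| 4 | 47-48% | 49 / 53 / 60% |
| 6 | 78-80% | 82 / 83 / 91% |
| 8 | 95-96% | 96 / 98 / 99% |
| 10 | 99% | 99 / 100 / 100% |

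If the added 20 points are lost in the same proportion as the rest, a 40-60% fall leaves 20 × 0.6 = 12 to 20 × 0.4 = 8 points. In that range the chi-square already has at least 95% power. In the model of Check 2 the crude difference was always at least 4.9 standard errors from zero.

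**Check 4: validity.** With no treatment effect, the chi-square rejected in 4.1-4.5% of simulated trials, against a nominal 5%.

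**The case against.** The strongest reply is that little depends on this. The chi-square is valid, it is the SAP's uniform method for binary secondary endpoints, and it would usually be significant anyway. The AT level at ICU admission is itself secondary objective 1, and its ANCOVA already uses baseline AT. In the simulation of Check 1 the ANCOVA had 77-96% power at a 4-point shift and at least 98% from 6 points, more than either binary analysis. All of this stands, and it limits the point to an optional gain. It does not supply what is missing: the ANCOVA estimates a mean difference, not the difference in the share clearing 58%, and no interval is promised for that share.

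A second reply concerns the remedy. The earlier trial had no treated patient below 58%. With an empty cell, the logistic treatment coefficient cannot be estimated by maximum likelihood. Replacing the chi-square and Fisher tests outright would leave no usable analysis in that case. This also stands, so the fix keeps those tests and adds a fallback.

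A reader might infer that baseline AT largely decides who reaches 58%. The documents give no figure for that. They stress dilution and consumption during bypass, and the amendment rationale says that patients starting at 80% or above can still arrive low. A reader might also take the 58% share as the direct test of whether the dose meets its target. It covers only one side of the range to be avoided. The 20-point dosing target is addressed by the AT samples before and after infusion.

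**Conclusion.** The point holds as a minor, free improvement. The 58% comparison has no adjusted estimate and no stated interval, although a covariate expected to be prognostic is already collected, defined and used in the same section.

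The loss is precision only. For assumed correlations of 0.3 to 0.8, the variance of the risk difference would fall by roughly 5% to 35-40%, or about 0.2 to 2 points of half-width. The size rests on a correlation that the documents do not give; at 0.3 the gain is close to negligible. A changed test result is plausible only if the effect at ICU admission is small and the correlation high.

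The documents do not support reading this as bias or as a failure of error control. Under randomization, chance imbalance in baseline AT is random error that the crude analysis already allows for.

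**What to change.** In SAP 10.2, keep the crude percentages and the chi-square or Fisher test for the 58% share, and add before unblinding:

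- A logistic model of AT at or above 58% at ICU admission on treatment and baseline central-lab AT, as already defined for the ANCOVA.
- The risk difference standardised over the mITT population (g-computation), with a 95% interval by the delta method or bootstrap; the SAP should name which.
- A fallback: if either arm has no or very few subjects on one side of 58%, report the unadjusted risk difference with an exact or score interval. The SAP should state the count that triggers it.

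The cost is a few sentences in the SAP and a short program. No new data are needed, and the quantity estimated is still the marginal risk difference between arms.

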5.1.3.2 Secondary Efficacy Analyses

Postoperative AT levels at the ICU admission will be summarized by treatment group. The analysis of covariance (ANCOVA) will be used to compare the treatment difference. ANCOVA model will include the AT level as dependent variable, treatment as fixed effect and baseline AT level as covariate. The similar approach will also be used to analyze the AT levels in other time points.

Postoperative chest-drain blood loss in the first 12 and 24 hours after surgery will be summarized by treatment group and will be analyzed using group t-test.

For transfusion requirements, Number of units of RBC, Number of units of FFP, and Number of units of platelets will be summarized by treatment group and analyzed using group t-test.

The number and percentage of subjects with each following procedure or morbidity will be separately summarized by treatment group and will be analyzed using Chi-square test (or Fisher Exact test as appropriate)

- Need for surgical reexploration
- Low cardiac output syndrome
- Myocardial infarction
- Stroke
- Acute kidney injury
- Arterial or venous thromboembolic events
- Infections
- Prolonged mechanical ventilation (>24 hours)

- All-cause postoperative mortality
- Prolonged ICU stay (>6 days)

Duration of ICU stay and the length of hospital stay will be summarized by treatment group. Non-parametric will be used to compare the treatment differences and Hodges-Lehmann estimation will be provided.

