- Central venous saturation (Swan Ganz / Central Venous Pressure (CVP) <60% with an arterial oxygen saturation of at least 90%.
- Cardiac Index <2.0 unresponsive to inotropic or mechanical support (catecholamine, intra-aortic balloon pump [IABP], etc.).
- Signs / symptoms of organ ischemia, such as: change in ST-segment or left ventricular wall motion abnormalities (LV).

Coagulation products:

Only if subject is bleeding 4 mL/kg/hour or more over at least 30 minutes or 1.5 mL/kg/hour or more over 2 consecutive hours.

- FFP (10-15 mL/kg) / PCC: If subject is actively bleeding and presents an international normalized ratio (INR) ≥ 1.5 .
- PLT: 1 apheresis unit or 4-6 pooled units if the PLT count is <100,000/ μ L.
- Cryoprecipitate / Fibrinogen concentrates: Administration of 8-10 units of cryoprecipitate or 2 grams of fibrinogen concentrate if the concentration of fibrinogen ≤ 1.5 g/L.

Shed blood collected during surgery can be retransfused according to institutional practice. Retransfusion of chest-drain collected blood is not permitted.

4. Percentage of subjects needing **surgical reexploration** defined as having to return to the operating room because of bleeding, tamponade, graft occlusion or any other cardiac reason will be considered from chest closure to the end of the follow-up period.
5. Percentage of subjects with **low cardiac syndrome** defined as the need for major inotropic support or intra-aortic balloon pump will be considered from the day of ICU admission and throughout the follow-up period.
6. Percentage of subjects with postoperative **MI** defined through enzymatic criteria plus new Q-waves at the electrocardiogram (ECG) will be considered from the day of ICU admission and throughout the follow-up period.

A perioperative MI is diagnosed by the following criteria:

- (0-24 hours postoperation):

The creatine phosphokinase-MB isoenzyme CK-MB (or creatine phosphokinase [CK] if MB not available) must be greater than or equal to 5 times the upper limit of normal, with or without new Q waves present in two or more contiguous ECG leads. No symptoms required.

- (>24 hours postoperation): Documented by at least one of the following criteria:

- a. Evolutionary ST-segment elevations
- b. Development of new Q-waves in two or more contiguous ECG leads
- c. New or presumably new left bundle branch block (LBBB) pattern on the ECG
- d. CK-MB (or CK if MB not available) ≥ 3 times the upper limit of normal

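### Chest-drain loss and transfusion units are tested without adjusting for baseline hemoglobin or weight, both already collected: a cheap gain in precision is left unused, though the planned tests are valid

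*SAP*

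**What the plan says.** SAP 10.2 states that chest-drain loss in the first 12 and 24 hours "will be listed, and will be summarized and analyzed using group t-test". Each blood product "will be summarized separately and analyzed using group t-test", with a non-parametric fallback that also has no covariate. Protocol 5.1.3.2 plans the same for drain loss, which "will be summarized by treatment group and will be analyzed using group t-test".

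AT levels are handled differently in SAP 10.2: "ANCOVA model will include the AT level as the dependent variable, treatment as the fixed effect and baseline AT level" as covariate. MI history, the only randomization stratum, is adjusted for in the primary Cochran-Mantel-Haenszel test (SAP 10.1) and nowhere else.

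The candidate covariates are on file. Hemoglobin is measured at the Screening and Preoperative visits (Protocol 3.6.2.2 and 3.6.2.3). Weight is recorded at Screening and determines the dose (SAP 3.1.1).

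The transfusion algorithm in SAP 4.2.2 sets red-cell rules by hemoglobin band, ending with "Hb >10.0 g/dL: Transfusion is not permitted". Red cells are given singly, "after which the hemoglobin (Hb) levels should be reanalyzed to check the suitability for the next unit". Coagulation products have a separate gate: "Only if subject is bleeding 4 mL/kg/hour or more over at least 30 minutes or 1.5 mL/kg/hour or more over 2 consecutive hours".

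**The concern.** Two routinely collected baseline values could plausibly predict these outcomes, and the planned tests use neither. For the same blood loss and dilution, a subject who starts with a lower hemoglobin reaches a transfusion band sooner, so baseline hemoglobin may well predict red-cell units. Drain loss is analysed in raw mL, and body size may account for part of its spread. Randomization is stratified by MI history only, so neither covariate is balanced by design.

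What is at stake is precision on a harm that the protocol itself raises. Protocol 1.1 reports 8 mL/hour more postoperative bleeding with AT in the earlier randomized trial, and Protocol 1.2 describes a dose-dependent trend towards more bleeding. Treatment-emergent bleeding events are summarized without a planned test (SAP 11.1). Drain loss and transfusion are therefore the main quantitative bleeding measures with a planned between-arm comparison. Any explainable variance left in the error term makes a real increase somewhat easier to miss.

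**Working it through.** **The plan's own figure.** The only sample-size statement (SAP 5.3) concerns the primary composite: 22.0% vs 14.3%, alpha 0.15, 70% power, 192 per arm. The unpooled formula, two-sided, gives (1.4395 + 0.5244)² × (0.22×0.78 + 0.143×0.857) / 0.077² = 191.4, so 192. The figure reproduces, but it says nothing about drain loss or transfusion. No SD, effect size or power is stated for either.

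**Inputs.** n = 192 per arm is the planning figure; the mITT number is not given. Tests are two-sided at 0.05, which is an assumption because the SAP sets no alpha for secondary outcomes. R² is also an assumption, shown as a range.

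**Formulas (linear model).**
- Adjusted SE = unadjusted SE × √(1 − R²)
- Equivalent n = n / (1 − R²)
- Adjusted power ≈ Φ[(1.96 + z) / √(1 − R²) − 1.96], where z = 0.524 for a starting power of 70% and 0.842 for 80%

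Example at R² = 10%, starting from 70%: (1.96 + 0.524) / 0.9487 − 1.96 = 0.659, and Φ(0.659) = 0.745.

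| Assumed R² | SE cut | Equivalent n per arm | 70% becomes | 80% becomes |
|---|---|---|---|---|
| 5% | 2.5% | 202 | 72% | 82% |
| 10% | 5.1% | 213 | 75% | 84% |
| 20% | 10.6% | 240 | 79% | 88% |

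**Scale for drain loss.** If the earlier 8 mL/hour excess lasted 12 hours, the difference would be 8 × 12 = 96 mL. Power = Φ[96 / (SD × √(2/192)) − 1.96], with SD multiplied by √0.9 for R² = 10%. The SDs are assumptions.

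| Assumed SD | Unadjusted | R² = 10% |
|---|---|---|
| 300 mL | 88% | 91% |
| 400 mL | 65% | 70% |
| 500 mL | 47% | 51% |

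**Limits of these figures.** The 1 − R² rule belongs to linear ANCOVA and is only a guide for a negative-binomial model of units. The drain model below uses weight and the MI stratum but not hemoglobin, so its R² need not match that of the red-cell model.

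**The case against.** The strongest reply is that nothing is wrong. With 1:1 randomization an unadjusted two-group comparison is valid, the protocol and SAP agree on it, and these are two of many unranked secondary outcomes in a phase 2b trial looking for trends. That stands: no bias or contradiction is shown. It limits the point to efficiency but does not remove it, because the covariates are already in the database.

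The gain is also unquantified by the documents and small if R² is small: at 5% it adds about two power points. That stands too.

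A reader might draw four stronger conclusions, which the documents do not support:

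- *That the algorithm ties red-cell transfusion to bleeding per kg.* It does not. The mL/kg/hour rule covers coagulation products only and says nothing about what predicts drain volume.
- *That the algorithm shows baseline hemoglobin to be a strong driver of units.* Its trigger is current hemoglobin, rechecked after each unit, with discretion in the middle bands. A predictive role for the baseline value is plausible inference and its strength is unknown.
- *That these outcomes are the trial's principal bleeding question.* No section says so. Bleeding risk is a separate safety variable (SAP 4.3.3), bleeding events are summarized over three windows (SAP 11.1), and reexploration for bleeding or tamponade is in the primary composite. The 8 mL/hour difference was judged not clinically significant by that trial's investigators, and it came from a 120% AT target.
- *That adjusting AT levels but not these outcomes is inconsistent.* AT has a pretreatment value of the same measurement; drain loss and units do not. The contrast shows only that the SAP accepts baseline adjustment in principle.

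**Conclusion.** The point holds as an improvement in efficiency. The planned tests for drain loss and transfusion are valid but may be less precise than they could be, since plausible predictors in hand are not used. With R² between 5% and 20%, a linear model gains the equivalent of 5% to 25% more subjects (1/0.95 − 1 to 1/0.80 − 1), and a comparison at 70% power rises to between 72% and 79%. These results rest on an assumed R², 192 per arm and two-sided 0.05. None of them is a stated property of the bleeding outcomes, and for the count model they are approximate. A reader who took the absence of covariates as an error, or as a source of bias, would be going beyond what the documents show.

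**What to change.** In SAP 10.2, before unblinding, prespecify:

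1. ANCOVA of 12-hour and of 24-hour chest-drain loss on treatment, screening weight and MI-history stratum, reporting the adjusted mean difference with 95% CI.
2. A negative-binomial model of red-cell units on treatment, baseline hemoglobin (SAP 5.1 definition: last non-missing value before study drug), screening weight and MI-history stratum, reporting the adjusted rate ratio with 95% CI.
3. The unadjusted comparison, retained and reported alongside each model.

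The cost is SAP wording and programming, with no new data. The transfusion paragraph needs editing in any case: its named fallback, the Wilcoxon signed rank test, is a paired procedure and does not fit two independent arms. The section also specifies a 95% CI for ICU and hospital stay but none for drain loss or transfusion, which items 1 and 2 would supply for drain loss and red-cell units.
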